**Protocol Title: A Prospective Controlled Treatment Trial for Post-Traumatic Headaches**

**NCT#: 03007420**

**Principal Investigator: [name]**

**A. SPECIFIC AIMS AND HYPOTHESIS**

**1. To compare the efficacy of Occipital Nerve Blocks (ONB) vs. Cervical Medial Branch Blocks (CMBB) in patients presenting with post-traumatic headache (PTH) who were non-responsive to previous interventional management.**

- To examine differences in Numeric Rating Scale (NRS) pain measurements (> 50% or < 50% pain reduction)
- To examine differences in Migraine Disability Assessment (MIDAS) and Pediatric Migraine Disability Assessment (PedMIDAS) scores
- To describe differences in functional outcomes using the Functional Disability Inventory (FDI) and the Pain Disability Index (PDI).
- To study differences in Quality of Life (QL) and Pediatric Quality of Life (PedsQL) scores

**Hypothesis:** Treatment with CMBB with steroids and lidocaine will be associated with a greater improvement in pain scores, functional and QL scores than the ONB.

**2. To describe the baseline socio-demographic characteristics of individuals with PTH and chronic axial neck pain.**

- To study gender, BMI, age, school and work absences and disrupted sleep
- To study psychological (anxiety, depression) and pain related comorbidities (whole body pain, gastrointestinal problems, small fiber neuropathy)
- To study correlation to nature of injury (concussion vs. head injury and severity of injury based on 1997 AAN guidelines)
- To study previous treatment methods and interventions

**Hypothesis:** Of the participants with PTH, the majority will exhibit school or work absences and disrupted sleep. The majority of participants will also have higher scores of anxiety and depression, more pain related comorbidities, history of prior injury, and previous treatment from other providers.

**3. To describe and understand how clinical features, physical exam characteristics, and radiologic findings among patients with PTH and axial neck pain associate with treatment response for each of the treatment options.**

- To assess physical exam characteristics (axial neck pain which is extension related, myofascial spasms and occipital neuralgia)
- To characterize the diagnosis given by the clinicians in their notes
- To characterize the presence of radiologic or predictive clinical findings such as facet arthropathy, disc changes, spondylolysis, or spondylolisthesis

**Hypothesis:** Treatment response (improvement in pain) will be associated with features on the physical exam (neck pain with extension, headaches associated with cervicogenic causes) and with presumed anatomic diagnosis (facet arthropathy, spondyloysis, spondylolisthesis, axial and discogenic pain).

**4. To study the effects of socio-demographic, clinical, and psychosocial predictor variables on CMBB and ONB treatment outcomes.**

**Hypothesis:** The likelihood of improvement with CMBB or ONB is associated with a combination of socio-demographic, clinical/anatomic, and psychosocial variables. Improved responses following treatment with ONB and CMBB will be associated with a shorter duration of pain prior to intervention, normal weight, younger age and lack psychological comorbidities.

**5. To study the safety of the ONB and CMBB treatment.**

- To study fluoroscopy time and amount of radiation exposure
- To study sedation method if any including the use of propofol, benzodiazepine or fentanyl vs. awake procedure
- To study anesthetic complications

**Hypothesis:** The time of fluoroscopy and radiation exposure will be low, and anesthetic complications or side effects will be minimal.

## **B. Background and Significance**

PTH is the most common physical symptom following concussion with up to 36% of athletes reporting headaches throughout the first year after concussion. PTH is defined as a secondary headache disorder through ICDH-3 criteria. There is an estimated 3.8 million sports related concussions in the US each year, and concussion has become an important global health issue in recent years. PTH pathophysiology is predominantly migrainous and cervicogenic in nature. Neurogenic inflammation after head injury can lead to activation of meningeal nociceptors and the trigeminovascular system leading to development of post-traumatic migraine. This can be secondary to direct injury of the trigeminal afferent nerves or to leptomeningeal or cerebrovascular structures innervated by trigeminal nerves. Activated glial cells, with increased production of pro-inflammatory substances have been implicated in the development and persistence of pain. The neuronal-glial signaling is suspected to play a role in sensitizing afferent trigeminal nociceptors. Prolonged inflammation and chronic hyper excitability are thought to predispose to a pathological pain state.

In addition, a common etiology of headache and neck pain in football related concussions is whiplash associated disorder (WAD), secondary to acceleration-deceleration injuries. Pain may be generated by inflammation of the high cervical facet joints, traumatic neuralgias and myofascial injury. Occipital headaches result from activation of the sensory branches of C2 and C3 peripherally, causing occipital neuralgia, with cervical facet inflammation and myofascial spasms resulting in cervicogenic headaches. The reported convergence of sensory C2 and the nucleus caudalis of the trigeminal nerve may result in exacerbation of post-traumatic migraines, and therefore treatment of cervicogenic headache etiologies could also improve post-traumatic migraines. The mechanism of overlap between the trigeminal nerve and the cervical nerves is known as convergence, whereby trigeminal nerve activation produces symptoms in the trigeminal and cervical territories and cervical activation produces symptoms in the cervical and trigeminal territory. In addition, multiple lifetime concussions in older and retired football players with

subsequent chronic cervical facet inflammation increase the risk of degenerative cervical arthritis and, therefore, the risk of cervicogenic headaches, which due to convergence also increases the risk of post-traumatic migraines.

Headache and neck pain following concussion are potentially treatable and resolve over time. Nerve blockade may enhance the recovery of appropriate neural circuits involved in the pathophysiology of chronic headache. Currently, no evidence-based guidelines exist for treatment of PTH. Adoption of "brain rest" for 1-2 weeks, followed by gradual return to activity and avoiding "second-impact syndrome" are current practice. The use of medications controlling neuropathic pain is of partial benefit for some patients and requires several weeks to evaluate, and as many take 4-6 weeks to show effect. Adverse effects like sedation, mood changes, cardiac side effects of pharmacologic agents are often not compatible with the demands of athletics. For those patients where sports performance is paramount, they may therefore not be able to tolerate typical medications. Incidence of chronic post-concussive headaches (> 3 months) at 1 year is 8.4% - 35% and at 4 years is up to 25%. Therefore, patients can have significant disability from their post-traumatic headaches for many years after their injury. Without appropriate treatment, these headaches can remain as chronic headaches. Over-the-counter and other symptomatic medication overuse can exacerbate and prolong PTH significantly, secondary to rebound headaches. Successful treatment is essential since PTH limits return to sports as well as more general activities of living, such as work and school. Most interventions currently in use partially help and take several weeks to months for noticeable benefit. Additionally, a multicenter, double-blind, placebo-controlled trial recently published in *The New England Journal of Medicine* showed no significant differences among amitriptyline, topiramate and placebo in reducing headache days or related disability after a 24-week period, and showed an increase in side effects (Powers et al, NEJM 2016). PTH interventions, including ONB and CMBB are used in the treatment of primary headache disorders and neck pain from cervical arthritis and may provide more improved, faster and more sustained pain relief in many patients. In addition, given that most of the action of the nerve blocks is local, there are significantly fewer side effects than in more typical headache medications. Injections that use corticosteroids may be beneficial in post-traumatic headache by reducing inflammation and therefore mechanical allodynia. Injection of corticosteroids in the cervical facet joint area has shown up to 13 months of pain relief. This prolonged effect may be

secondary to central pain modulation. Ultimately, nerve blocks may be a more effective and efficient post-traumatic headache given the onset of effect and the minimal side effects.

To date, there have been no prospective studies of procedural treatments for medically refractory PTH and none in the adolescent and young adult population in whom football injuries are common. Despite the frequent clinical practice of using ONB and CMBB for occipital neuralgia, cervical arthritis and cervicogenic headaches, there has been no adequate scientific investigation into the use of these interventions for PTH. Given that PTH is typically felt to be secondary to inflammatory reaction to trauma, the use of injection of corticosteroids may be more effective in PTH than in typical headache disorders. There is also no adequate comparison of these interventions to medications.

### **C. PRELIMINARY STUDIES**

There are no preliminary studies comparing the effect of interventions and medications on PTH to date.

### **D. DESIGN AND METHODS**

#### **1. Study Design**

We propose a randomized, controlled clinical trial and prospective follow up to evaluate the effect of invasive procedures in the management of PTH. Adolescents and young adults will be recruited from Boston Children's Hospital, Beth Israel Deaconess Medical Center, and Mass General Brigham Pain clinics, Concussion clinics and Headache clinics. Patients will be recruited beginning July 2017.

We propose to study the effect of CMBB versus ONB treatment with lidocaine and steroids. Patient demographics (e.g. age, sex, ethnicity, and race), disease characteristics (e.g. symptoms, duration of the disease, medications taken, etc.), and description of the intervention will be collected. As part of the standard of clinical care at the study sites, patients will complete the intake Standard Pain Questionnaire at baseline. During the first two months of the study, patients will be contacted by our research team via email on a weekly basis requesting them to complete a study questionnaires. After the initial 2 months on the study, we will continue to contact patients every 2 weeks over the next 10-months. Patients will remain in the study up to 12 months after enrollment.

#### **2. Patient Selection and Inclusion/Exclusion Criteria**

Patients who meet the criteria below will be recruited from Boston Children's Hospital, Beth Israel Deaconess Medical Center, and Mass General Brigham Pain clinics, Concussion clinics and Headache clinics.

**Inclusion Criteria:**

- Age 14 – 45 years.
- History of post-traumatic headache or neck pain following a concussion or head injury within the last 2 years.
- Self-reported lack of meaningful benefit with at least one previous treatment trial. Previous treatment could include a migraine prophylactic medication, a neuropathic pain medication, a physical intervention, or a cognitive-behavioral intervention.

**Exclusion Criteria:** Subjects will be excluded in the following circumstances:

- Significant underlying psychological concerns, as determined by study psychologist up on review of standardized assessment
- Lack of parental consent and child assent (if patient age <18 years) or lack of consent (if patient age >18 years). Unable to complete the questionnaire, based on parental or patient estimation of cognitive or language limitations

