## **I. Data Analysis Plan and Sample Size**

At the time of data analysis, datasets will be downloaded from both REDCap and InForm and merged into Statistical Analysis Systems 9.3 for purposes of analysis. Missing data will be accounted for when the data is coded into respective variables.

In order to detect a 30% difference between treatment groups, and with an  $\alpha$  of 0.05 and  $\beta$  of 0.8, we will need a sample size of 24 subjects per group. Taking into consideration a 30% dropout rate during the study, we estimate a sample size of 63 subjects in the trial.

We will analyze pain scores (NRS), MIDAS/ PedMIDAS, FDI and QL scores as continuous variables. Differences of these parameters from baseline will be the outcomes variables. The differences in pain, functional, and QL scores will first be tested for normality. Assuming normality, T-Tests will be conducted to investigate the differences between the two randomized

groups. If data does not appear to be normal, Wilcoxon Rank Sum Tests will be performed in contrast to T-Tests.

Descriptive statistics will be generated in order to summarize socio-demographic characteristics of study participants. Frequency tables will be generated to describe gender, psychological and pain related comorbidities, history of injury, previous treatment methods and interventions. Similarly, frequency tables will be generated to depict physical exam characteristics, presumed anatomic diagnosis provided by clinicians, and presence of any predictive clinical findings. Continuous characteristics such as age and BMI will be tested for normality using the Shapiro-Wilk test. Continuous characteristics will be summarized using mean and standard deviation if the distribution appears normal, or will be summarized using median and interquartile range if the distribution does not appear normal. We will evaluate baseline differences between responders and non-responders, using chi-square and t-test for categorical and continuous variables, respectively.

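### Time since injury varies from no stated minimum to 2 years and is expected to be prognostic, yet the NRS comparison of ONB with CMBB neither adjusts for it nor stratifies on it

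*Combined protocol and SAP*

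**What the plan says.** **Entry.** The inclusion criteria (section D.2) require "History of post-traumatic headache or neck pain following a concussion or head injury within the last 2 years" and "Self-reported lack of meaningful benefit with at least one previous treatment trial". No minimum time since injury, minimum pain duration, minimum baseline score or run-in is stated.

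**Natural history and prognosis.** Section B states: "Headache and neck pain following concussion are potentially treatable and resolve over time". It also reports: "Incidence of chronic post-concussive headaches (> 3 months) at 1 year is 8.4% - 35% and at 4 years is up to 25" per cent. Aim 4 hypothesises: "Improved responses following treatment with ONB and CMBB will be associated with a shorter duration of pain prior to intervention".

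**Population wording.** Aim 2 concerns "individuals with PTH and chronic axial neck pain". Section B places the study among medically refractory cases.

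**Data.** Section D.1 lists disease duration among the characteristics collected. Section E (Other Independent Variables) records pain before the intervention in months.

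**Allocation and analysis.** Section D.3 describes randomisation to the two procedures and mentions no stratification. Section I takes differences from baseline as the outcomes and says "T-Tests will be conducted to investigate the differences between the two randomized" groups, with a Wilcoxon rank sum test if the data are not normal. It adds a repeated-measures comparison and a multiple regression on treatment and broad classes of patient characteristics. Duration is not named, and neither model is designated as the main treatment comparison.

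**The concern.** The criteria allow a patient a few weeks after a concussion and a patient close to two years to be compared on the same change score. By the protocol's own account their expected course may differ whichever block they receive. Two things follow in a trial of this size. First, a chance excess of recent injuries in one arm shifts that arm's mean change, and an unadjusted test has no means of removing the shift. Second, differences in course between early and late patients add to the spread of the change scores, so the comparison is less precise than it could be. Both can be reduced with a variable the trial already collects. The plan does not commit to using it in the comparison that matters most.

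**Working it through.** **The plan's own figures.** Section I gives 24 per group for a 30% difference, alpha 0.05 and a value of 0.8 printed as beta and read here as power. It states no SD or response rates, so 24 cannot be reproduced from its inputs. Taking 24 per arm, two-sided 0.05 and 80% power as given, the t-test needs a standardised difference of 0.83 SD. The total of 63 matches 48 × 1.3 = 62.4, rounded up. The calculations below use 24 per arm.

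**Is the test biased?** No. Simulated t-tests (20,000 trials per setting, 24 per arm, 0% to 40% of patients given an extra fall of 1.0 SD regardless of arm, no true difference between blocks) rejected in 4.7% to 5.3% of trials.

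**How likely is a chance imbalance?** Let p be the share of recent injuries. The documents do not give it, so it is an assumption. With simple randomisation the counts in the arms are independent Binomial(24, p). A gap of 5 patients is 5/24 = 20.8 percentage points, and 6 patients is 25 points.

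| p | P(gap of 5 or more patients) | P(gap of 6 or more) |
|---|---|---|
| 20% | 10% | 5% |
| 30% | 16% | 8% |
| 40% | 18% | 10% |
| 50% | 19% | 11% |

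**What would such a gap do?** Let g be the extra mean fall in recent-injury patients, in SD units, also assumed. The shift in the between-arm difference is gap × g. With a gap of 0.208, g = 1.0 gives 0.21 SD and g = 1.5 gives 0.31 SD. Against the 0.83 SD the trial is sized to detect, that is 25% and 38%, in either direction.

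**What does the added spread cost?** The SD of the change score becomes sqrt(1 + p(1 − p)g²). At p = 30% and g = 1.0 this is sqrt(1 + 0.21) = 1.10. The standardised difference is then 0.826/1.10 = 0.75, and power at 24 per arm is 72%.

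| p | Power, g = 1.0 | Power, g = 1.5 |
|---|---|---|
| 20% | 74% | 67% |
| 30% | 72% | 64% |
| 40% | 71% | 62% |

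These figures assume the planning SD of 1 refers to patients of similar duration. If it already describes the mixed population, there is no shortfall against plan. Adjustment would then be a gain in precision over the planned test.

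**The case against.** **Analyses already planned.** The regression includes treatment and clinical characteristics, and duration is recorded, so an adjusted estimate could be produced. That is true, but the covariates are not named and the regression is not the designated comparison. What is missing is a commitment, not data.

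**Randomisation and the t-test already allow for chance imbalance.** This stands for the type I error. A reader might infer that the arms will be systematically unbalanced on duration; the documents give no ground for that. What remains is a loss of precision, and the risk of an awkward imbalance in this one trial.

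**The failed-treatment criterion screens out recent injuries.** In part. Section B says of medications that "as many take 4-6 weeks to show effect", so a proper drug trial implies some weeks. But the criterion rests on self-report, sets no minimum length and accepts physical or cognitive-behavioural treatment.

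**Dilution.** A reader might go further and infer a large power loss because some patients recover whichever block they get. If a share f does so and the whole 0.83 SD effect sits in the others, power is 71%, 61%, 50% and 39% at f = 10%, 20%, 30% and 40%. The documents do not support treating these as estimates. They give no recovery rate by time since injury, and section I states its difference between the treatment groups as enrolled, which may already include such patients. Neither stratification nor adjustment would cure dilution in any case.

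**Broad entry is defensible.** Aim 4 studies duration as a predictor, and truncating the range would remove part of what it studies. Section B also notes that disability can last for years. The 3-month figure there qualifies an incidence statistic, and *chronic* in Aim 2 describes the neck pain. The absence of a lower limit is therefore not shown to be an error. Aim 4 itself is a hypothesis about both blocks, not an established fact.

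**Conclusion.** The point holds as one of precision and prespecification. A variable that the protocol expects to be prognostic, and already records, is left out of both the allocation and the stated between-arm test. At 24 per arm, with 30% recent injuries assumed, there is about a 16% probability of a gap of roughly 21 percentage points or more. For an assumed extra fall of 1.0 to 1.5 SD, a gap of that size moves the estimate by 0.21 to 0.31 SD. Power might fall from 80% to somewhere between 62% and 74% through added spread, but only under the assumed p and g and only if the planning SD ignored mixed durations. The documents fix none of these quantities.

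Two matters of wording and reporting remain. The references to chronic neck pain (Aim 2) and medically refractory headache (section B) describe a narrower group than the criteria admit. And because neither arm is untreated, any association between short duration and good response under Aim 4 cannot be separated from natural recovery.

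**What to change.** - In section I, make the between-arm NRS comparison a model, either ANCOVA at a stated time or the repeated-measures model already planned. Prespecify treatment, baseline NRS and months of pain (or months since injury) as terms. Keep the t-test or Wilcoxon test as a supporting analysis if wanted.
- In section D.3, stratify randomisation by time since injury, for example at the 3-month mark used in section B, and carry that factor or its continuous form into the model.
- Reconcile the chronic and medically refractory wording with the inclusion criteria. Whether a minimum duration should apply is the investigators' decision; the protocol should state and justify it either way.
- State under Aim 4 that a duration-response association cannot be distinguished from natural recovery in this design.

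The cost is one extra stratum in a small trial, one covariate already collected and some text. The changes reduce chance imbalance and recover precision to the extent that duration predicts outcome. They do not restore any effect lost to patients who would recover under either block.

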**3. Description of Study Treatments or Exposures/Predictors**

Patients enrolled in the study will be randomized to receive either an ONB (Figure 2, additional procedure details provided below) with dexamethasone 2mg each site with 3ml 1% lidocaine, for a total of two sites or a CMBB (Figure 3a & 3b, additional procedure details provided below) with dexamethasone 1.5mg each site with 2 ml 1% lidocaine, for a total of three sites on each side. The assignment of the procedure will be randomized however neither the patients nor the investigator will be blinded to the procedure. If patients exhibit a  $\geq 50\%$  pain reduction on receiving the block evaluated after four weeks, then they may continue to receive blocks as needed, but not more than one every three months. If patients exhibit  $< 50\%$  pain reduction, the patient will be treated as per the clinician's judgment with the possibility of a cross over to the other treatment option in the protocol.

All patients will be followed for 12 months after enrollment and after the crossover of treatments they will continue to be treated and followed per clinical standard of care.

As part of this study, patients will need to complete 8 follow-up visits, of which the first and second will be in-person clinical visits and the other follow-ups could either be conducted in-person at the clinic or via teleconference - video:

a) Visit 1: in-person clinic visit

- At the first visit to the clinic, the physician or nurse will verify the patient's name and date of birth, and will collect information about pain, current and past medicines, and general health. The physician will perform a physical examination and measure heart rate, blood pressure and respiratory rate, and conduct a neurological exam.
- Baseline questionnaires will be taken, including Pain (NRS), Concussion Symptom Score, MIDAS/PedMIDAS, Anxiety, Depression, FDI, and QL.

At the end of the visit, all enrolled patients will be randomized to one of the two minimally invasive procedures, the ONB or the CMBB. Information from the patient's most recent clinical visit note (retrieved from the patient's medical record) may be used to obtain Visit 1 data.

b) Visit 2: Cervical and medial branch block procedures

The procedure will be performed at Boston Children's Hospital or Beth Israel Deaconess Medical Center or Mass General Brigham Operation Room. Patients may receive sedation as per clinical need, and procedures will be performed in a standardized manner. Neither the patient nor the investigator will be blinded to the type of procedure.

Patients will not be universally sedated however a particular subset of patients may receive sedation. Pediatric patients and some adults with extreme anxiety to procedures will receive mild IV sedation with fentanyl, midazolam and occasionally propofol. This is not general anesthesia but is Monitored Anesthesia Care (MAC). Patients will be awake enough to report any symptoms or discomfort. Anesthesia will be administered either in an Operating Room or Day Surgery Unit setting of the study sites and not in an outpatient setting. A separate anesthesia team consisting of an anesthesiologist and nurse anesthetist (CRNA) will be responsible for administration of anesthesia and airway maintenance. Vital signs will be monitored every 5 minutes and anesthesia adjusted based on patient discomfort.

Details on doses of dexamethasone and lidocaine to be used:

Dexamethasone doses:

Occipital nerve block: 2 mg / block

Cervical facet injections/medial branch block: 1.5 mg / facet joint

Lidocaine doses:

Occipital nerve block: 3 ml of 1% lidocaine / block

Cervical facet injections/medial branch block: 2 ml of 1% lidocaine / facet joint

DESCRIPTION OF OCCIPITAL NERVE BLOCK:

The patient will be in the seated position. The back of the head (occipital area) will be prepped with alcohol pads. Following this, the left or right greater occipital nerve will be accessed at the midpoint of the occipital protuberance and the mastoid process using a 25-gauge 1-1/2 inch needle. 1% lidocaine will be used for skin and subcutaneous analgesia. Following this, area of the left greater occipital nerve will be accessed and the injection fanned. A mixture of 2 mg of dexamethasone and 3 ml of 1% lidocaine will be injected into this area. Following this, the contralateral side will be addressed in a similar fashion (if patient needs bilateral injection). A total of 4 mg of dexamethasone and 6 mL of 1% lidocaine will be injected. The patient will be observed in recovery for complications of bleeding, worsening of symptoms, or paresthesias.

DESCRIPTION OF CERVICAL FACET / MEDIAL BRANCH BLOCK:

The patient will be placed in the prone position in the procedure room on a Steris table with fluoroscopy. The back of the neck will be prepped and draped in the usual sterile fashion with ChloraPrep. Under fluoroscopy guidance the high cervical facets will be visualized in AP, oblique and lateral views. Using a 22-gauge, 2-1/2-inch spinal needle, the left C 4-5 facet joint/medial branch area will be accessed under fluoroscopy. 1% lidocaine will be used for the skin and subcutaneous analgesia. Contrast omnipaque 300 mg/ ml, 0.5 ml will be used to confirm the needle position. Similar procedures will be repeated at C2-3 and C 3-4 levels. Similar procedures will be done on the corresponding levels on the contralateral side. Dexamethasone 1.5 mg with 2 mL of 1% lidocaine will be injected at each of these levels. A maximum of 9 mg of dexamethasone will be used. The patient will be observed in recovery for complications of bleeding, worsening of symptoms or paresthesias.

After the procedure is completed, all patients will recover in the Post Anesthesia Care Unit (PACU). Patients will be examined and they will be required to complete questionnaires. Patients will be discharged from the hospital per hospital guidelines and standard of clinical practice.

c) Visit 3 to 8: in-person visit or tele-conference

At 1, 2, 3, 6, 9, and 12 months after enrollment, patients will be evaluated to determine how well they did after the procedures. This would include the same steps from previous appointments. If the study treatment has been helpful, the physician might decide to continue the treatment with the procedures as needed. Clinical criteria and patient – physician agreement would be used to determine next steps in the patient's treatment plan.

d) E-mail questionnaires:

During the first two months of the study, patients will be contacted by our research team via email on a weekly basis requesting them to complete a short questionnaire that includes questions about their pain scores (NRS), MIDAS/ PedMIDAS, QL, FDI, Anxiety, Depression, and Concussion Symptoms Score. After the initial 2 months on the study, we will continue to contact patients every 2 weeks over the next 10-months (follow-ups over a total of 12 months). See Table 1 below for REDCap survey schedule.

[figure not shown]
Table 1: Schedule of REDCap surveys

Follow-Up	Questionnaire
Week 0	Migraine disability
	Pain Assessment
	Concussion Score
	General functionality
	Quality of Life
	Anxiety
	Depression
Week 1	Pain Assessment
	Concussion Score
	General Functionality
	Side Effects Related to Invasive Treatment
Week 2	Pain Assessment
	Concussion Score
	General Functionality
	Side Effects Related to Invasive Treatment
Week 3	Pain Assessment
	Concussion Score
	General Functionality
	Side Effects Related to Invasive Treatment
Improvement Evaluation 1m	Pain Assessment
	Concussion Score
	General Functionality

[figure not shown]
	Side Effects Related to Invasive Treatment Improvement Additional Procedures
Week 5	Pain Assessment Concussion Score General Functionality Side Effects Related to Invasive Treatment
Week 6	Pain Assessment Concussion Score General Functionality Side Effects Related to Invasive Treatment
Week 7	Pain Assessment Concussion Score General Functionality Side Effects Related to Invasive Treatment
Improvement Evaluation 2m	Pain Assessment Concussion Score General Functionality Side Effects Related to Invasive Treatment Quality of Life Anxiety Depression Improvement Additional Procedures
Week 10	Pain Assessment Concussion Score General Functionality Side Effects Related to Invasive Treatment
Improvement Evaluation 3m	Migraine disability Pain Assessment Concussion Score General Functionality Side Effects Related to Invasive Treatment Quality of Life Anxiety Depression Improvement Additional Procedures
Week 14	Pain Assessment Concussion Score General Functionality Side Effects Related to Invasive Treatment
Week 16	Pain Assessment Concussion Score General Functionality

	Side Effects Related to Invasive Treatment
Week 18	Pain Assessment Concussion Score General Functionality Side Effects Related to Invasive Treatment
Week 20	Pain Assessment Concussion Score General Functionality Side Effects Related to Invasive Treatment
Week 22	Pain Assessment Concussion Score General Functionality Side Effects Related to Invasive Treatment
Improvement Evaluation 6m	Migraine disability Pain Assessment Concussion Score General Functionality Side Effects Related to Invasive Treatment Quality of Life Anxiety Depression Improvement Additional Procedures
Week 26	Pain Assessment Concussion Score General Functionality Side Effects Related to Invasive Treatment
Week 28	Pain Assessment Concussion Score General Functionality Side Effects Related to Invasive Treatment
Week 30	Pain Assessment Concussion Score General Functionality Side Effects Related to Invasive Treatment
Week 32	Pain Assessment Concussion Score General Functionality Side Effects Related to Invasive Treatment
Week 34	Pain Assessment Concussion Score General Functionality Side Effects Related to Invasive Treatment
Improvement Evaluation 9m	Migraine disability Pain Assessment

	Concussion Score General Functionality Side Effects Related to Invasive Treatment Quality of Life Anxiety Depression Improvement Additional Procedures
Week 38	Pain Assessment Concussion Score General Functionality Side Effects Related to Invasive Treatment
Week 40	Pain Assessment Concussion Score General Functionality Side Effects Related to Invasive Treatment
Week 42	Pain Assessment Concussion Score General Functionality Side Effects Related to Invasive Treatment
Week 44	Pain Assessment Concussion Score General Functionality Side Effects Related to Invasive Treatment
Week 46	Pain Assessment Concussion Score General Functionality Side Effects Related to Invasive Treatment
Improvement Evaluation 12m	Migraine disability Pain Assessment Concussion Score General Functionality Side Effects Related to Invasive Treatment Quality of Life Anxiety Depression Improvement Additional Procedures

**Figure 1:** Study design for a prospective controlled trial in posttraumatic headaches

**Figure 2: Occipital nerve blocks (ONB).** (Adapted from Waldman SD. *Atlas of interventional Pain Management*. 2nd ed. Philadelphia: Elsevier; 2004.) The ONB site of injection is determined at the midpoint of the line joining the mastoid process and external occipital protuberance.

**Figure 3a:** Cervical medial branch block (CMBB) posterior approach targeting the medial branch of the dorsal ramus of the spinal nerves

**Figure 3b:** Cervical medial branch block (CMBB) posterior approach fluoroscopy view

